4.4 Sample size calculation

The sample size will be 140 (N = 70 in each of the conditions), with 15% oversampling to compensate for attrition. On the basis of an expected meta-analytic effect size of r = .24 for the VIPP interventions (Juffer et al, 2010, 2017), power is $\geq .82$ (G*Power 3.1.9). This sample size provides also sufficient power to test indirect effects through hormone levels and neural processing, as the power of the test of indirect effects is (substantially) greater than the power of the test of direct effects (Kenny & Judd, 2014).

Version number: 5, 06-02-2018 19 of 46

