7. METHODS

7.1 Study parameters/endpoints

7.1.1 Main study parameter/endpoint

The main study parameters are:

- Parenting behavior, including physiological response to infant stimuli ("handgrip task"), sensitivity ("quality of care"), involvement ("quantity of care"), and protection.
 We will examine the effects of VIPP-PRE on these parenting behaviors.
- Activity in brain areas associated with parenting. We will examine the effects of VIPP-PRE on activity in these areas in fathers during the processing of infant signals and brief video vignettes designed to elicit protective parenting.
- Oxytocin, vasopressin, and estradiol levels will be assessed in saliva. Cortisol and testosterone will be assessed in both saliva and hair samples. Saliva samples are used to measure current hormonal levels. Hair samples provide information on hormone levels in past period: as human scalp hair grows approximately 1 cm per month, hormone concentrations in 1 cm hair reflect the mean exposure of 1 month.

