For the "protection" task and protection questionnaire, a GLM examining the betweengroup differences in within-subject (pre- and posttest) effects.

If applicable, *p*-values will be corrected for multiple comparisons using a Bonferroni correction.

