10.2 Recruitment and consent

A total of 140 fathers (2 x 70) will be recruited to take part in the study, with 15% oversampling to compensate for attrition. All recruitment and consent procedures listed below have recently been approved by the CCMO (document nr NL54702.058.15). Similarly to our pilot study (see NL54702.058.15), we will recruit through midwife agencies with the use of a recruitment letter (Document E3.1). Also, participants will be recruited using social media (e.g. Facebook), websites (e.g. the Leiden University website), and flyers (e.g. at pregnancy fairs, see Document E3.2), as was done in the pilot study (see NL54702.058.15). Eligible families will receive an invitation to participate in the study (Document E1.1). This invitation includes information about the study and a response card to express their interest for participation.

Interested fathers will receive a letter with detailed information about the study (Document E1.3) and will be informed that they will receive a phone call in a week. During this phone call, a research assistant will check the inclusion and exclusion criteria and answer questions. All interested fathers who reach us through other means (e.g. social media) will be sent an email with more information about the study (Document E1.2). Information collected from fathers who are excluded due to the outcome of the 20-week ultrasound will be deleted.

During all visits and sessions the fathers have the opportunity to ask questions before the intervention or measurement starts. Questions arising during the intervention or the lab visits will be answered as adequately as possible.

Written informed consent (IC) for participation, including fMRI measures, collection of saliva and hair, and the use of video/audio recordings collected during assessments (i.e. LISSA, sensitivity with own infant, and FMSS), will be obtained from the participant during the first lab visit (see Document E2.1 for the fathers' IC form). Both parents provide consent for participation of the infant, including the use of video recordings collected during assessments as well as the ultrasound images (see Document E2.1, and

Version number: 5, 06-02-2018

Document E2.2 for the partners' IC form). The consent forms will be stored in a locked filing cabinet accessible only to the investigators. At the time of consent, any remaining questions will be answered.

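### The single power figure in section 4.4 matches one uncorrected test, while all behavioural, neural and hormonal measures are primary under a Bonferroni rule with no defined family

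*Protocol*

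**What the plan says.** **Power.** Protocol section 4.4 states: "The sample size will be 140 (N = 70 in each of the conditions), with 15% oversampling to compensate for attrition". It takes an "expected meta-analytic effect size of r = .24 for the VIPP interventions" and reports power of at least .82 from G*Power. It gives no outcome, alpha, sidedness or adjustment for multiple tests.

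**Main outcomes.** Section 7.1.1 lists three groups as main study parameters. The first opens "Parenting behavior, including physiological response to infant stimuli" and also covers sensitivity, involvement and protection. The second is brain activity during infant signals and threat videos. The third is hormonal: "Oxytocin, vasopressin, and estradiol levels will be assessed in saliva. Cortisol and testosterone will be assessed in both saliva and hair samples". No measure is placed above the others. The only secondary item, in 7.1.2 and 9.2, is moderation by early childhood experiences.

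**Multiplicity.** Section 9.1, on the primary parameters, plans cluster-corrected whole-brain analyses alongside region-of-interest and connectivity analyses, and general linear models for the other outcomes. It ends by saying that, where applicable, p "values will be corrected for multiple comparisons using a Bonferroni correction". It does not say which tests form the family or when the correction applies.

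**The concern.** One power figure stands beside a long, unranked list of primary measures and a correction whose use is left open. A reader of 4.4 would assume that each main outcome is tested with power of at least .82. That cannot hold on the 4.4 basis once alpha is divided, even by two. If alpha is not divided, nothing limits the chance of a false positive across the primary tests, apart from the whole-brain imaging. Because the condition for correcting is not defined, the choice could be made after the results are known.

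The stake is interpretation. A positive result could come from any of the main measures. A null result on a corrected test would come from a test with less power than the protocol advertises.

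**Working it through.** **Inputs.** N = 140, 70 per arm, and r = .24 (section 4.4). Alpha is not stated; two-sided .05 is assumed because it reproduces the stated power.

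**Step 1: the protocol's own figure.** For two equal groups, d = 2r/√(1 − r²) = .48/√.9424 = .494. The noncentrality is d√(N/4) = .494 × √35 = 2.925. With 138 degrees of freedom and a critical t of 1.977, power is .828. Fisher's z gives .817 and the normal approximation .833. The stated figure is therefore that of one uncorrected test with all 140 analysed.

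**Step 2: how many primary measures.**
- Handgrip: 1
- Sensitivity (free play, speech sample, infant simulator; section 7.3): 3
- Involvement (self-report, partner report, e-diary): 3
- Protection (startle task, questionnaire): 2
- fMRI paradigms: 2
- Hormones (five in saliva, two also in hair): 7

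The total is 1 + 3 + 3 + 2 + 2 + 7 = 18. Adding the separate own-infant observation (7.3) and the partner report on quality of care (9.1) gives 20. Brain regions, contrasts and connectivity are not counted. A coarser count is three domains, or six if the four behaviours are separated (4 + brain + hormones).

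**Step 3: Bonferroni at .05/k, two-sided, noncentral t.** The 119 column is 140 × .85, which applies only if the 15% loss falls inside the 140. The last column is 1 − .95^k, the uncorrected chance of at least one false positive among independent tests.

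| k | Power, 140 analysed | Power, 119 analysed | Uncorrected error |
|---|---|---|---|
| 1 | .828 | .763 | 5% |
| 2 | .744 | .665 | 10% |
| 3 | .692 | .606 | 14% |
| 6 | .599 | .507 | 26% |
| 18 | .455 | .365 | 60% |

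**Step 4: sensitivity to the assumptions.**
- *One-sided alpha.* One-sided .05 gives .897 for one test at N = 140, which also satisfies the stated bound. At .05/k it gives .828, .780, .692 and .544 for k = 2, 3, 6 and 18, so the shortfall begins at three tests.
- *Baseline adjustment.* With the baseline as covariate, d becomes d/√(1 − ρ²). At an assumed ρ = .5 this is .494/.866 = .571, and power is .83, .76 and .63 for k = 3, 6 and 18. At ρ = .7 it is .95, .92 and .85.
- *Group-by-time test.* With two time points this is a test of change scores, and d becomes d/√(2(1 − ρ)). At ρ = .5 the divisor is 1, so the table's figures do not change. The gain therefore depends on the form of the model as well as on ρ.

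**The case against.** The case for the protocol has force in several places.

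- **The .82 is correctly computed.** A reader might infer an arithmetic error in 4.4. There is none: the figure reproduces, and 4.4 does not claim power after correction.
- **The protocol fixes no divisor.** A reader might infer that the trial's power is .60 or .46. The documents do not support that, because the correction is conditional and the family undefined. Section 2 frames three hypotheses and 7.1.1 has three groups, so correction by domain is as natural a reading as correction over 18.
- **A two-sample t test is not the planned analysis.** Section 9.1 plans pre/post models and 9.3 adds covariates. A high pre-post correlation could offset part or all of the loss. But the protocol gives no such correlation, and the startle task and own-infant observation have no prenatal baseline.
- **Some multiplicity is already handled.** Whole-brain analyses are cluster-corrected. The 60% figure assumes independence; several measures tap one construct, and positive correlation would lower it.
- **Attrition may lie outside the 140.** Section 10.2 says "A total of 140 fathers (2 x 70) will be recruited to take part in the study, with 15% oversampling to compensate for attrition", which can mean recruitment on top of 140. The 119 column is only one reading.
- **An analysis plan may define the family.** That is possible, and that document is not at hand. It would not remove the mismatch between the unqualified power figure in 4.4 and the unranked primary list in 7.1.1.

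These points limit the size of the problem. They do not supply the missing link between the power figure, the primary measures and the correction.

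**Conclusion.** The point holds as a matter of multiplicity and stated power. The .82 in section 4.4 is reproduced by one two-sided test at .05 with all 140 fathers analysed. The protocol attaches it to no outcome, and sections 7.1.1 and 9.1 make every measure primary.

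If Bonferroni is applied across the primary measures, per-test power on the 4.4 basis is below the stated figure from two tests upward: .74, .69, .60 and .46 for 2, 3, 6 and 18. If it is not applied, error across the primary tests outside the whole-brain analysis is uncontrolled, at up to 14%, 26% and 60% for 3, 6 and 18 tests if these are independent.

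The figures rest on an inferred two-sided alpha, a post-only comparison and an assumed number of tests. They are per-test powers; the chance that at least one test succeeds is higher. It would go too far to conclude that a null trial would be uninformative or that the trial must recruit more fathers. The size of the shortfall depends on a family the protocol does not define, and naming the primary outcome resolves it at the present sample size.

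**What to change.** 1. In 4.4, tie the .82 to one named outcome tested at two-sided .05, and give the lower power at the corrected alpha for the other main measures.
2. In 9.1, replace the conditional wording with a defined family and a Bonferroni or Holm rule, fixed before the data are seen.
3. In 7.1.1, have the sponsor name one primary outcome, or a small set with a stated split of alpha, and move the rest to secondary.

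Which outcome to choose is the sponsor's scientific decision. Observed sensitivity is a natural candidate, since section 5.1 says the intervention targets it. If the own-infant observation is chosen, it has no prenatal baseline and needs a between-group comparison instead of the pre/post model in 9.1.

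The cost is protocol wording and no extra fathers. The downside is that the stated power for the other outcomes becomes less favourable.

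### Section 9.1 names single-step Bonferroni, although Holm's step-down gives the same family-wise guarantee and never rejects fewer hypotheses: a cheap improvement

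*Protocol*

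**What the plan says.** The multiplicity rule is the closing sentence of protocol section 9.1: "If applicable, *p*-values will be corrected" and, as to method, "corrected for multiple comparisons using a Bonferroni correction". That sentence does not say which tests form a family or how many there are.

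The main parameters in section 7.1.1 are numerous. The parenting behaviours are the handgrip response plus "sensitivity ('quality of care'), involvement ('quantity of care'), and protection". Brain activity and hormone levels follow, and section 2 names five hormones.

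Section 4.4 plans 70 fathers per condition, "with 15% oversampling to compensate for attrition". It bases a power of at least .82 on an "expected meta-analytic effect size of r = .24 for the VIPP interventions". It states neither the significance level nor a multiplicity adjustment.

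**The concern.** Bonferroni compares every p-value in a family of m with .05/m. Holm orders the p-values, compares the smallest with .05/m, the next with .05/(m − 1), and so on, and stops at the first failure. Both procedures limit the chance of any false rejection to .05 without assumptions about how the outcomes are correlated. Holm's thresholds are never stricter, so Bonferroni can only match it or reject fewer hypotheses.

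This is relevant here because the objectives expect effects in several domains, and Holm gains when more than one effect is real. What is at stake is some power for the second and later real effects. The validity of the trial is not in question.

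**Working it through.** **Inputs.** From section 4.4: n = 70 per arm and r = .24. Assumptions: two-sided .05 (no level is stated); the 15% oversampling comes on top of 140, so 140 are analysed; one simple two-group test per outcome; a family of m = 4, taken from the four behavioural domains in 7.1.1; outcome correlation between 0 and .5.

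**1. Reproduce the plan's own figure.**
- d = 2r/√(1 − r²) = .48/√(1 − .0576) = .494
- Noncentrality = d·√(n/2) = .494 × √35 ≈ 2.92
- Power at two-sided .05: .833 by normal approximation, .828 by exact noncentral t, .817 by Fisher z.

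These agree with the stated .82. A one-sided test would give .889 to .900, so the stated figure matches a single, unadjusted two-sided test.

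**2. Why Holm is never worse.** With m = 4, Bonferroni's threshold is .05/4 = .0125 for every outcome. Holm's are .0125, .0167, .025 and .05 in order of p-value. An outcome with p ≤ .0125 passes at whatever rank it has, because all smaller p-values also pass. For the error bound, suppose m₀ hypotheses are truly null. The first null to be rejected is compared with at most .05/m₀, so the chance of any false rejection is at most m₀ × .05/m₀ = .05 under any dependence. In the simulations Holm never rejected fewer hypotheses than Bonferroni.

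**3. Power per real outcome, m = 4** (simulation with normal test statistics; small differences are Monte Carlo error):

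| Real effects of 4 | Bonferroni | Holm | Any false rejection at correlation 0, Bonferroni → Holm |
|---|---|---|---|
| 1 | .67 | .67 | .036 → .045 |
| 2 | .67 | .69 | .024 → .040 |
| 3 | .67 | .72–.73 | .012 → .033 |
| 4 | .67 | .75–.78 | none possible |

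The ranges cover outcome correlations from 0 to .5. By exact t, single-test power at .0125 is .653 rather than about .67.

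**4. Check by hand (independent outcomes, normal approximation).** Single-test power is .665 at .0125 and .702 at .0167, a difference of .037.
- Two real effects: Holm helps one effect mainly when the other has passed at .0125. The gain is about .665 × .037 = .025, so .665 becomes .690, as simulated.
- One real effect: Holm helps only if one of the three nulls is falsely rejected first, with chance 1 − .9875³ = .037. The gain is about .037 × .037 = .001.

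**5. Chance of at least one rejection.** This is identical by construction, because Holm's first step is the Bonferroni test.

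**6. Other family sizes (correlation 0, r = .24 for every real effect).**
- m = 5: .635 → .655 with two real, .638 → .757 with all five.
- m = 8: .576 → .611 with four real, .577 → .704 with all eight.
- m = 12: .524 → .559 with six real, .525 → .645 with all twelve.

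With one real effect the gain is about .001 at each of these sizes.

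**The case against.** The strongest objection is that this is a preference. Bonferroni is valid under any dependence, simple, and gives matching simultaneous confidence intervals. Section 9.1 makes no claim that Holm would falsify. All of that is true, and it is why the point is only an improvement. It does not remove the point: 9.1 itself fixes the method, the alternative dominates it for testing, and the protocol plans no simultaneous intervals that would favour Bonferroni.

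A second objection concerns the figures. The family of four is an assumption, because 9.1 names none. The planned tests do not count neatly to four: quantity of care has three sources, protection has a task and a questionnaire, and cortisol and testosterone are each measured in saliva and hair. The planned models are repeated-measures GLMs, whose power depends on within-subject correlations that the protocol does not give. Section 4.4 gives r = .24 for VIPP interventions generally, with no separate figure for hormones. All of this stands. The sizes are illustrations; the dominance of Holm depends on none of them.

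Four stronger readings are tempting and not supported:
- **The stated power is wrong.** It reproduces for a single unadjusted test and does not rest on either procedure.
- **Bonferroni costs the fall from .83 to about .67.** That fall comes from correcting for four tests at all. Holm recovers only part of it and stays below .82 in every corrected scenario above.
- **Holm adds power with no extra error.** It shares the bound, but the realised rate rises within it, for example from .024 to .040 with two of four effects real.
- **The all-effects-real gain is the expected gain.** The protocol does not say how many effects to expect, and it sets no criterion that all outcomes must succeed.

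**Conclusion.** The point holds as a cheap improvement. For hypothesis tests, Holm has the same guaranteed family-wise bound and rejects at least as much, whatever the family turns out to be. In the illustrative family of four, power per real outcome rises by about 2 points with two real effects, 5 to 6 with three, and 8 to 11 with four. It does not change materially with one. These sizes rest on r = .24 for every real effect, 140 fathers analysed, two-sided .05 and a simple two-group test.

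Nothing in the protocol is invalid or contradictory on this point. A reader might also infer that Holm settles the conditional wording and the unnamed family in 9.1. It does not, because Holm needs a defined family just as Bonferroni does. That definition may sit in the analysis plan, which is not at hand.

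**What to change.** In section 9.1, replace Bonferroni correction with Holm step-down (Bonferroni-Holm) correction, applied to whatever family of tests the plan corrects. Make the change before outcomes are compared between arms. The cluster correction that 9.1 already plans for the whole-brain analyses stays as it is.

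The cost is one phrase, with no additional fathers or measurements. The downsides are that simultaneous confidence intervals are less direct than with Bonferroni, and that more of the .05 error allowance is used.

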9.2 Secondary study parameter(s)

To investigate potential moderation by fathers' early life experiences, additional analyses will be conducted, including the interaction between intervention condition and fathers' early life experiences.

9.3 Other study parameters

Analyses will be adjusted for pertinent covariates (e.g., sports, food and drinks at assessment days and the day before: see 7.1.3)

9.4 Interim analysis (if applicable)

Not applicable

10. ETHICAL CONSIDERATIONS

10.1 Regulation statement

The study will be conducted according to the principles of the Declaration of Helsinki (Tokyo, 2004) and in accordance with the Medical Research Involving Human Subjects Act (WMO). The protocol of this study will be submitted to the "Commissie Medische Ethiek" (CME), Leiden Universitair Medisch Centrum, and the study will not commence before formal approval has been granted.

10.2 Recruitment and consent

A total of 140 fathers (2 x 70) will be recruited to take part in the study, with 15% oversampling to compensate for attrition. All recruitment and consent procedures listed below have recently been approved by the CCMO (document nr NL54702.058.15). Similarly to our pilot study (see NL54702.058.15), we will recruit through midwife agencies with the use of a recruitment letter (Document E3.1). Also, participants will be recruited using social media (e.g. Facebook), websites (e.g. the Leiden University website), and flyers (e.g. at pregnancy fairs, see Document E3.2), as was done in the pilot study (see NL54702.058.15). Eligible families will receive an invitation to participate in the study (Document E1.1). This invitation includes information about the study and a response card to express their interest for participation.

Interested fathers will receive a letter with detailed information about the study (Document E1.3) and will be informed that they will receive a phone call in a week. During this phone call, a research assistant will check the inclusion and exclusion criteria and answer questions. All interested fathers who reach us through other means (e.g. social media) will be sent an email with more information about the study (Document E1.2). Information collected from fathers who are excluded due to the outcome of the 20-week ultrasound will be deleted.

During all visits and sessions the fathers have the opportunity to ask questions before the intervention or measurement starts. Questions arising during the intervention or the lab visits will be answered as adequately as possible.

Written informed consent (IC) for participation, including fMRI measures, collection of saliva and hair, and the use of video/audio recordings collected during assessments (i.e. LISSA, sensitivity with own infant, and FMSS), will be obtained from the participant during the first lab visit (see Document E2.1 for the fathers' IC form). Both parents provide consent for participation of the infant, including the use of video recordings collected during assessments as well as the ultrasound images (see Document E2.1, and

Version number: 5, 06-02-2018

Document E2.2 for the partners' IC form). The consent forms will be stored in a locked filing cabinet accessible only to the investigators. At the time of consent, any remaining questions will be answered.

In order to obtain permission for using the video material made in this study (i.e. LISSA, free play with infant, and VIPP-PRE / ultrasound images) for education and training purposes, both fathers and their partners will receive an additional consent form (Document E2.3).

10.3 Objection by minors or incapacitated subjects (if applicable)

Not applicable

10.4 Benefits and risks assessment, group relatedness

There are no risks associated with the assessments used in this study.

Auditory Startling Task

The short sound fragment used in the Auditory Startling Task is not harmful for the hearing of both father and infant.

MRI

No adverse effects have been reported in participants/patients undergoing MRI at the currently available field strengths. Participants will be protected against any procedural risks via a thorough pre-screening process. Structural MRI scans will be inspected by a radiologist, and in case of visible abnormalities the participant, participant's physician, and researcher will be notified. Participants' data will be handled strictly confidentially, except as required by law.

VIPP

This study concerns a behavioural intervention and not a medical trial. Several RCT's have shown the effectiveness of the VIPP intervention in improving parental sensitivity and have shown that VIPP interventions have no harmful effects (see Juffer et al., 2008). Both fathers (Lawrence, Davies and Ramchandani, 2012) and mothers (Stolk et al., 2008) have responded positively to the intervention. Parents report positive changes in parent-child interactions, parental wellbeing, and relationship quality when they were both present during the intervention (Iles et al., 2017).

Prenatal ultrasound

Ultrasound devices are unrelated to adverse maternal, perinatal or childhood outcomes (e.g. impaired physical or neurological development; see Hershkovitz et al., 2002; Torloni et al., 2009), and are considered to be safe. Scanning time in this study remains within the range of recommended scanning times (see BMUS, 2010; Harris et al., 2016; see also section 6).

Although there is no direct benefit to the participants from the proposed research, there are greater benefits to society from the potential knowledge gained from this study. Once we understand the neurobiological underpinnings of good-enough and poor parental sensitivity and protection, better attempts can be made to improve parenting and reduce the adverse effects of poor parenting. The proposed study is ground-breaking in that it includes paternal protection, an important dimension of parenting that has been neglected in all imaging studies and virtually all behavioral studies of parenting to date, maybe because of the almost exclusive focus on mothers. Furthermore, real-time measures using apps and mobile phones have been underused in research and may provide data with high ecological validity, that may differ considerably from data collected retrospectively using traditional questionnaires on time spending. Thus, the importance of the benefits gained from this research outweighs the minimal risks involved.

The privacy of individuals who participate in scientific research is protected in the Dutch Data Protection Act. The VSNU Association of Universities in the Netherlands has written a code of conduct for the use of personal data based on this law. Data will be handled strictly confidentially. Data will be stored in a confidential manner, both through the use of a numbering system and through the security of the files and computer systems. Only the researchers and research assistants have access to the data. According to the Dutch Data Protection Act, Dutch organizations can appoint a data protection officer (art. 62), but are not legally required to do so. Leiden University has chosen for a personal data contact person, who in addition to the Ethics Review Board reviews the data collection procedures. Moreover, Leiden University has a "Leiden Research data office" (http://www.library.leiden.edu/teaching-researching-publishing/publish-deposit-research/data-management/leiden-research-data-office.html) with expertise to inform and advise us in all phases.

